1.1 Introduction

Dry eye disease (DED) is a common condition that causes ocular discomfort and reduces visual acuity.[1] The two categories of dry eye disease are evaporative dry eye and aqueous deficient dry eye.[2] Both conditions can involve pathology of the meibomian glands, lacrimal glands, lids, tear film, and surface cells.[2, 3] Meibomian gland dysfunction (MGD) is the leading cause of evaporative dry eye[4] and contributes to aqueous deficient dry eye.[5]

Meibomian glands are modified sebaceous glands located along the upper and lower eyelid margins. Twenty to forty glands are located along each lid[6] and secrete meibum, the lipid component of tears.[7] MGD is defined by the International Workshop in Meibomian Gland Dysfunction[4] as the chronic, diffuse abnormality of the meibomian glands, commonly characterized by terminal duct obstruction and/or qualitative/quantitative changes in the glandular secretion. Patients may experience symptoms of eye irritation and clinically observable ocular surface disease and inflammation due to alteration of the tear film.

MGD is a commonly encountered disease by ophthalmologists. The impact of dry eye on quality-of-life is comparable to the effect of moderate to severe angina or dialysis treatment.[8, 9] The goal of MGD therapy is to provide long term improvement of symptoms for patients by improving the quality of meibum, increasing meibum flow, improving tear film stability, and decreasing inflammation. Commonly used therapies include preservative free drops, omega-3 fatty acid supplementation, topical cyclosporine, serum tears, topical azithromycin, oral doxycycline, moisture chambers, intraductal probing, lid margin exfoliation, automated thermal pulsation, warm compresses, and others. Despite the variety of treatment options available, patients often do not experience complete or long term relief of symptoms. Forced meibomian gland expression was first described in 1921 by [name] as an effective method of rehabilitating meibomian glands and improving dry eye symptoms in his patient.[10] The eyelid margins are forcefully compressed to express gland contents. Korb et al described an improvement in lipid layer thickness and symptoms in 10 patients with meibomian gland dysfunction treated with MGX.[11] Forced manual expression is painful for patients, and some of them are unable to tolerate the pain.

1.2 Intense Pulsed Light Therapy

Intense pulsed light (IPL) devices have long been used in the field of dermatology to treat acne rosacea, acne vulgaris, hyperpigmentation, essential telangiectasias, unwanted hair, and photodamaged skin. IPL is a high-intensity light source consisting of visible light in the wavelength range of 515–1200 nm. The light is both polychromatic and incoherent.[10] Most IPL dry eye patients receive this treatment as a last resort after trying several other therapies. They often have severe MGD and few to no expressible glands. Treatments are spaced four to six weeks apart, and patients typically receive one to four treatments with no established limit on the number of quarterly maintenance treatments.

Given that the majority of dry eye syndrome is due to MGD, IPL/MGX treatment would theoretically be successful in improving symptoms in the majority of dry eye patients. For this reason, off-label IPL/MGX treatment was attempted to achieve symptom relief even when no significant ocular rosacea was detected in refractory dry eye syndrome in very symptomatic patients who had exhausted traditional modalities of dry eye treatment.

The specific mechanism of IPL therapy in improving dry eye symptoms is unknown. However, various hypotheses exist based on dermatological studies. It is postulated that oxyhemoglobin in blood vessels located on the surface of the skin absorbs light emitted from the flashlamp. The absorption generates heat that coagulates the red blood cells, leading to thrombosis of the blood vessels.[11-14] Several studies have examined changes in inflammatory regulators with the use of IPL. For instance, when using IPL for aged skin, Huang et al (2011) found an upregulation of MMP-1 and a downregulation of TGF-B1; while El-Domyati et al (2015) found no change in TGFB levels with IPL. In studies using IPL for acne vulgaris skin treatment, Ali et al (2013) found an upregulation of TGF-B1 and Taylor et al (2014) found a downregulation of TNFa expression and no change in IL-10 or IL-8. Nevertheless, more data is needed to elucidate these mechanisms, and to our knowledge, no studies examining cytokine changes with the use of IPL for DED have been published.

There are approximately 40 centers performing IPL nationally; however, specific guidelines on selecting the ideal IPL candidate have not been published. Two peer-reviewed studies have been reported to date on the efficacy of combined IPL/MGX for treating MGD as [name], the ophthalmologist who introduced IPL to dry eye patients, has described.[11-15] In his three-year retrospective review of 91 patient records, Toyos et al. found a statistically significant improvement in tear film break up time (TBUT, p=0.000). Physician-judged improvement in meibum and lid margins was present in 94% and 98% of patients, respectively. Eighty-seven percent of patients showed improvement in clinical signs and 93% had subjective amelioration of their evaporative DED. Thirteen percent of patients experienced an adverse event. Voros and Gupta conducted a retrospective review of 37 patient records and found a statistically significant decrease in scoring of lid margin edema, facial telangiectasia, lid margin vascularity, and improvement in meibum quality score (P<0.001). They also found a significant increase in oil flow score and TBUT (P<0.001), and a significant decrease in ocular surface disease index scoring (P<0.001).

Several prospective trials have been conducted on the efficacy of IPL (without MGX) for treating MGD. Craig et al. (2015) reported that IPL alone was effective in improving the lipid layer and patient symptoms.[16] In 2016, Jiang [17] enrolled 40 patients to receive IPL on day 1, day 15, day 45 and day 75. When compared to baseline measurements, significant improvements were found in both subjective symptomatic assessments and objective measurements of Meibomian gland secretion quality, TBUT, and conjunctival injection. While this study provided evidence of the benefit of IPL on MGD, its presents some limitations including a lack of control group and no analyses of inflammatory markers, or tear cytokines. In 2016, Gupta et al [18] conducted a cohort study of 100 patients with the diagnosis of MGD and DED who underwent an average of 4 IPL sessions. They reported a significant decrease in lid margin edema, lid margin vascularity, meibum viscosity and OSDI score, in addition to a significant increase in oil flow score and TBUT. Furthermore, in our previously published retrospective chart review of 35 patients with DED who were treated with serial IPL/MGX, we found a significant improvement in dry eye symptoms in 89% of patients and improvement in meibomian gland function in 77% of patients.[19]

1.3 Adverse Events

Previous studies have failed to show significant adverse events with the use of IPL for MGD or DED. Jiang et al's (2016) prospective study reported no change in visual acuity, no change in intra ocular pressure (IOP), no changes to pigmentation and no blistering, swelling, redness or hair loss at the surface.[17] A similar lack of adverse events was found in Gupta et al (2016).[18] Additionally, our 2016 retrospective study found IPL to be well tolerated among participants.[19]

1.4 Summary and Hypothesis

Given the aforementioned data and relative lack of prospective studies regarding the use of MGX/IPL in patients with DED, we propose a prospective, randomized, case-controlled clinical pilot study to examine the efficacy of IPL for both subjective and objective measures. 20 patients with DED will be recruited, and will be randomly assigned to one of two groups: MGX alone, or MGX with IPL, and will undergo treatment every 4-6 weeks for 4 total treatment. Subjectively, participants will be scored using dry eye symptom questionnaires, including the OSDI, prior to treatment and post-treatment. Objective measures at baseline and at the end of the study will include tear cytokine levels, impression cytology for inflammatory markers, meibography, tear osmolarity, and ocular microbiome testing (see Chapter 2).

We hypothesize that use of MGX with IPL will lead to greater improvement in subjective dry eye symptoms, improved objective meibomian gland measures, and an upregulation in tear cytokines such as TGF-B1 and downregulation of inflammatory markers, such as IL-10, and improvement of ocular microbiome load, as compared to participants treated with MGX alone.

Given the lack of adverse effects reported in the literature, we do not anticipate study participants will experience adverse effects with proper performance of the IPL and testing procedures. For IPL subjects, masking using IPL-aid for both eyes will be used to protect the ocular structures. After Fitzpatrick skin type assessment, test application of IPL will be performed at the right preauricular skin and evaluated for erythema or skin change prior to

proceeding with the rest of the IPL application. We will record all events and include them in our analyses.

Chapter 2: Study Overview and Design

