2.4 Data Collection and Analysis

Appointment 1/Baseline. Data will be collected on the participants first visit ("baseline") and will include the following: OSDI, visual acuity, slit lamp imaging, lissamine green staining, fluorescein, tear film break up time (TBUT), Schirmers 5 minute with anesthesia osmolarity, meibography, Keratograph5 redness evaluation, Lipiview lipid tear film thickness, , tear cytokine evaluation and impression cytology (for flow cytometry of labeled cells for inflammatory markers), and tear sample for ocular microbiome testing.

number identifier, and their data will be entered into an Excel Document ("data file") and RedCap database which will be kept on a secure server at Mayo Clinic Arizona.

[figure not shown]
At appointment 1, participants will receive the initial treatment of either MGX or MGX+IPL. At appointment 1, participants will be given Tobramycin-Dexamethasone ophth soln to use BID topically OU for 2 days, and told to avoid UV exposure for 3 weeks.

Appointment 2. 4-6 weeks after appointment 1, at appointment 2, participants will be evaluated using OSDI, visual acuity, Icare tonometry, slit lamp imaging, lissamine green staining, fluorescein staining. This data will be entered into the data file. Participants will receive their second treatment of either MGX or MGX+IPL. At appointment 2, participants will be given Tobramycin-Dexamethasone ophth soln BID for 2 days, and told to avoid UV exposure for 3 weeks

Appointment 3. 4-6 weeks after appointment 2, at appointment 3, participants will be evaluated using OSDI, visual acuity, Icare tonometry, slit lamp imaging, lissamine green staining, fluorescein staining. This data will be entered into the data file. Participants will receive their second treatment of either MGX or MGX+IPL. At appointment 3, participants will be given Tobramycin-Dexamethasone ophth soln BID for 2 days, and told to avoid UV exposure for 3 weeks

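### Section 1.4 expects no adverse effects because the literature shows none, yet section 1.2 cites 13% with IPL/MGX and section 1.1 reports MGX pain; events are to be recorded, but without structured ascertainment

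*Combined protocol and SAP*

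**What the plan says.** Four places in the combined protocol and SAP bear on risk.

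- Section 1.4 bases its expectation on the literature: "Given the lack of adverse effects reported in the literature, we do not anticipate study participants will experience adverse effects". The sentence goes on to make this conditional on correct performance of the IPL and the tests. MGX is not named.
- Section 1.3 makes a qualified statement: "Previous studies have failed to show significant adverse events with the use of IPL for MGD or DED". It draws on a prospective study, a cohort study and the investigators' own retrospective series, which it describes as well tolerated.
- Section 1.2 introduces two studies of the combined treatment ("Two peer-reviewed studies have been reported to date on the efficacy of combined IPL/MGX for treating MGD") and reports for the 91-record review: "Thirteen percent of patients experienced an adverse event". Section 1.3 does not mention this figure.
- Section 1.1 says of MGX: "Forced manual expression is painful for patients, and some of them are unable to tolerate the pain".

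On detection, section 1.4 undertakes to record every event and include it in the analysis, and has a test IPL application checked for skin change before the rest is given. Section 3.2 names visual acuity and intraocular pressure as safety measures. Section 2.4 lists the assessments by visit; at appointments 2 and 3 "participants will be evaluated using OSDI, visual acuity, Icare tonometry, slit lamp imaging, lissamine green staining, fluorescein staining". Appointment 4 includes the final treatment, and section 2.4 explains why no fifth visit is planned.

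**The concern.** A protocol should not expect no adverse effects on the strength of a literature that, by its own account, includes a 13% event rate with the experimental treatment. Nor should its risk statement omit the one procedure that every patient receives, when its introduction says that some patients cannot tolerate it.

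The premise matters more because the promise to record all events is not carried into the written visit lists. No definition, grading, fixed question or time window is given. Section 2.3 masks only the laboratories and the data analyst, and section 7.0 describes no sham IPL. Patients probably know their arm, so unprompted reporting could differ between arms. A low recorded count would then be hard to interpret and might be taken to confirm section 1.4. There is also an efficacy aspect: the comparison isolates IPL only if MGX is delivered alike in both arms, and no written item records whether MGX was completed.

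**Working it through.** The documents give no safety calculation to reproduce. The check sets the stated expectation against the protocol's own cited rate.

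**Inputs**
- Adverse-event rate: 13% (section 1.2).
- Denominator: 91 records (section 1.2).
- Arms: 10 MGX + IPL and 10 MGX alone (section 2.3).
- Treatments per patient: four (sections 6.0 and 7.0).
- MGX intolerance: stated in section 1.1 without a rate, so it cannot be quantified.

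**Count behind the 13%.** 0.13 × 91 = 11.83. 12/91 = 13.2%, which rounds to 13%; 11/91 = 12.1% does not. The count of 12 is inferred, not stated.

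**If 13% applied to the 10 IPL patients (assumption)**
- Expected patients with an event: 10 × 0.13 = 1.3.
- P(no event) = 0.87^10 = 0.248.
- P(at least one) = 1 − 0.248 = 0.752, or 75%.

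**Range.** The exact (Clopper-Pearson) 95% interval for 12/91 is 7.0% to 21.9%.
- At 7.0%: P(at least one in 10) = 0.516.
- At 21.9%: P(at least one in 10) = 0.916.

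**What zero events would show.** With 0 of 10, the one-sided 95% upper limit is 1 − 0.05^(1/10) = 0.259. A clean IPL arm would therefore still be compatible with a true rate of up to about 26%, and at a true 13% it would occur one time in four (0.248).

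**Exposure.** MGX: 20 × 4 = 80 sessions. IPL: 10 × 4 = 40 sessions. No visit is planned after treatment four, so 20 of the 80 MGX sessions and 10 of the 40 IPL sessions have no scheduled follow-up.

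**Do the planned measures cover the two risks?**
- *Test IPL application:* checked before the rest of the IPL, so it does not describe the skin after full treatment.
- *Visual acuity, tonometry, slit lamp imaging and staining:* eye measures; they record neither facial skin reactions nor procedural pain. Tonometry is listed at appointments 2 and 3 only.
- *OSDI (section 4.1):* asks about the past week, whereas visits are 4 to 6 weeks apart, so it cannot capture pain at the previous session.
- *WHOQOL-BREF (section 4.2):* asks how far physical pain in general limits the patient over four weeks. It is not a record of procedural pain, and it is not in the written visit lists.

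This reading covers the written lists only; a figure in section 2.4 is not shown in the available text.

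**The case against.** The strongest reply is that the protocol does not ignore safety. It undertakes to record and analyse all events, checks a test application and names two safety measures. Staff perform every treatment and would see immediate pain, intolerance or redness. The case report form is not among the documents and may hold the items that the visit lists lack. All of this stands. A reader might infer that the trial looks for neither risk, that recording rests on spontaneous report alone, or that curtailed MGX would go unseen. The documents do not support those readings. They show only that no structured item is specified.

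A reader might also infer that section 1.3 is false. It is not shown to be. It speaks of significant events, and section 1.2 gives no type, severity or attribution for the 13%, so both can be true. Nor does section 1.3 set out skin effects to look for; it lists effects that one earlier study found absent. Section 1.4's sentence makes no claim about MGX, so section 1.1 exposes an omission, not a contradiction.

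Finally, the 13% comes from one three-year retrospective review, and the number of sessions per patient is not given. The protocol also cites a 40-patient prospective study and a 100-patient cohort with no such effects reported, and the investigators' own 35-patient IPL/MGX series. This limits how far the 75% can be pressed. It does not rescue section 1.4, which asserts a lack of reported adverse effects without qualification.

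**Conclusion.** The point holds as a wording conflict together with an ascertainment gap. Section 1.4's unqualified premise conflicts with the rate cited in section 1.2, and its risk statement omits the MGX pain stated in section 1.1. On the cited rate, an event among the 10 IPL patients is more likely than not: 1.3 expected, 75% chance of at least one, 52% to 92% over the interval.

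Those figures assume that the review's rate transfers to this trial, that patients are independent, and that 12 patients lie behind the 13%. They say nothing about severity or about whether IPL or MGX was the cause. The MGX part cannot be sized from the documents. Differential reporting by arm is plausible where no sham is described, but it is an inference. The change is worth making before enrolment; it does not call the design into question.

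**What to change.** 1. Reconcile sections 1.3 and 1.4 with sections 1.2 and 1.1. Cite the 13% beside the other series, with its limits (one retrospective review; severity, type and attribution not given), and state the known MGX pain. Do not write an expected number of events into the protocol as fact.
2. In both arms, record on the existing case report form at every treatment session a pain score, whether MGX was completed, and any visible skin reaction immediately after treatment. The timing matters: a skin check only at the next visit, 4 to 6 weeks later, would miss short-lived reactions.
3. In both arms, ask the same fixed adverse-event question, covering the whole interval since the last treatment, at appointments 2 to 4. Ask it once more after treatment four by a brief remote contact, which avoids the fifth visit that section 2.4 expects patients not to attend.

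The cost is a few minutes per visit and one short contact per patient, 20 in all. More minor events will be counted, and the stated risk will look less favourable. No treatment or dose changes.

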2.2 Participant Exclusion Criteria

Several exclusion criteria will be included in order to ensure selection of patients who lack systemic conditions, or whose DED is not expected to change due to severity. Subjects without ocular rosacea will be excluded. Participants will be excluded solely based on the following factors: dry eye symptoms that are not alleviated with topical anesthetic (indicating possible neurotrophic eye pain), presence of systemic conditions including Graft versus Host Disease (GVHD) or Stevens - Johnson syndrome (SJS), and/or presence or history of alkali burns. Additionally, participants who wear contact lenses will be excluded, any participant with evidence of >50% MGA, or any participant with prior history or concurrent treatment for DED in the past 6 months.

2.3 Participant Randomization

Once inclusion criteria have been met, patients will be randomized to one of two groups using a random number generator. 10 patients will be randomized to the control group, in which they will receive MGX every 4-6 weeks; and 10 patients will be randomized to the treatment group, in which they will receive MGX and IPL every 4-6 weeks. Biomarker and microbiome labs and data analyzer will be masked to treatment group.

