Appointment 4. 4-6 weeks after appointment 3, at appointment 4, participants will be evaluated with the following: OSDI, visual acuity, slit lamp imaging, lissamine green staining, fluorescein, tear film break up time (TBUT), Schirmers 5 minute with anesthesia osmolarity, meibography, Keratograph5 redness evaluation, Lipiview lipid tear film thickness, , tear cytokine evaluation and impression cytology (for flow cytometry of labeled cells for inflammatory markers), and tear sample for ocular microbiome testing. Participants will receive their final treatment of either MGX alone or MGX + IPL. At appointment 4, participants will be given Tobramycin-Dexamethasone ophth soln BID for 2 days, and told to avoid UV exposure for 3 weeks. (Data from Vegunta et al (2016) [19] proved that 3 treatments alone are sufficient to produce a symptomatic MGX/IPL response with improvement of dry eye symptoms and signs. We did not expect that subjects would be compliant to return for a 5th appointment if there was no treatment being performed at that visit.)

Data Analysis. After the completion of 4 treatments, and the collection of data as outlined above, data will be analyzed using statistical methods for changes to the aforementioned tests. The analysis will be conducted by a research trainee who will be blinded to the participant groups. That is, they will receive the identifiers "Group 1" vs "Group 2", without the identification of which group received MGX/IPL vs MGX alone.

ÌPL)

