3.2 Objective Parameters

Visual Acuity (VA). VA will be recorded in Snellen format for each eye as a safety measure. We hypothesize no changes to VA will be seen between groups. Cost for VA is estimated at \$20 for each test and will be bundled into OPH EST LIMITED EXAM CPT (see 3.3 below).

Applanation tonometry (TA). Recorded intraocular pressure (IOP) for each eye as measured by Goldmann applanation tonometry. IOP measurement and recording is a safety measure. We hypothesize no changes to IOP will be seen between groups. Cost for TA is estimated at \$20 for each test and will be bundled into OPH EST LIMITED EXAM CPT (see 3.3 below).

Conjunctival Injection Score (Redness). Analyzed using slit lamp images from Keratograph 5. Increased injection has been associated with increased DED symptoms. Score is graded as 0-3, with 0 being no conjunctival injection and 3 being marked injection. We hypothesize a decrease in conjunctival injection score with MGX/IPL versus MGX alone. Cost for conjunctival injection scoring is estimated at \$20 for each test and will be bundled into OPH EST LIMITED EXAM CPT (see 3.3 below).

Lissamine Green staining of the interpalpebral conjunctiva. Conjunctival staining is an effective tool to examine epithelial damage. It is easy to perform and has been proven with good reproducibility. We hypothesize an improvement in conjunctival staining with the use of MGX/IPL versus MGX alone. Two areas will be graded from 0-3 in severity. Cost for lissamine green staining is estimated at \$20 for each test and will be bundled into OPH EST LIMITED EXAM CPT (see 3.3 below).

Fluorescein Cornea Staining (FCS). Corneal staining is an effective tool to examine epithelial damage. It is easy to perform and has been proven with good reproducibility. We hypothesize an improvement in corneal staining with the use of MGX/IPL versus MGX alone. Five areas

each will be graded from 0-3 in severity. Cost for FCS is estimated at \$20 for each test and will be bundled into OPH EST LIMITED EXAM CPT (see 3.3 below).

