Meibography Keratograph. Meibography is a tool to measure the amount of meibomium gland atrophy (MGA). MGA has been reported to be an important cause of dry eye.[27, 28] Images are objectively measured using ImageJ (NIH) based on a previously published report. [29] Results are reported from 0-100% atrophy of total surface area. We hypothesize a significant improvement in MGA with MGX/IPL versus MGX alone. Cost for meibography is estimated at \$20 for each test and will be bundled into OPH EST LIMITED EXAM CPT (see 3.3 below).

Lipiview. Lipiview measures lipid tear film thickness by interferometry on Lipiview instrument. Results are reported on a scale from 20-100. We hypothesize a decrease in the absolute thickness of tear film lipid layer with MGX/IPL versus MGX alone. Cost for lipiview is estimated at \$20 for each test and will be bundled into OPH EST LIMITED EXAM CPT (see 3.3 below).

Tear Cytokine. Tears will be collected at baseline and after the third treatment to be analyzed for the following markers: IL-1B, IL-6, IL-8, IL-10, IL-17, IFNg, TNFa, and TGFB1. Tear cytokine analysis of these markers has previously been shown as a marker of ocular surface inflammation, and is upregulated in DED.[30-33] We hypothesize an increase in TGFB1 and a decrease in the aforementioned inflammatory cytokines with MGX/IPL versus MGX alone. Samples will be collected at baseline and frozen at -80*C until analyzed using a pre-made custom plate (Millipore, USA). For 40 samples (20 patients x 2 samples each (1 pre and 1 post treatment), we will require 1 96-well plate at the cost of \$1500 + \$260 service fees. Additionally, to analyze TGFB1, we will require a separate plate at the cost of \$500 + \$300 for all samples. Therefore, the final cost for tear cytokine analysis will be \$2,560 for all samples for the entirety of the study.

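### The masking list covers the laboratories and the data analyst but not whoever scores the redness and meibography images, so two outcomes expected to favour IPL can be read with the arm known

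*Combined protocol and SAP*

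**What the plan says.** Section 2.3 gives the masking provision in one sentence: "Biomarker and microbiome labs and data analyzer will be masked to treatment group". Section 2.4 explains the analyst's part: "The analysis will be conducted by a research trainee who will be blinded to the participant groups". The method is to pass on results under two neutral group labels. No other section extends masking to participants, treating staff, examiners or image readers.

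Two outcomes in section 3.2 are derived from images. Redness is described as "Analyzed using slit lamp images from Keratograph 5", and "Score is graded as 0-3, with 0 being no conjunctival injection and 3 being marked injection". For gland atrophy, "Images are objectively measured using ImageJ (NIH) based on a previously published report". Neither entry names a reader or asks for coded or masked reading. Both carry a direction: "We hypothesize a decrease in conjunctival injection score with MGX/IPL versus MGX alone", and "We hypothesize a significant improvement in MGA with MGX/IPL versus MGX alone".

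Section 2.4 schedules both measurements at appointments 1 and 4 only. Section 6.0 gives the IPL arm eye shields and roughly 30 to 40 pulses before expression. Section 7.0 gives the control arm expression alone, with no sham pulse.

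**The concern.** Giving the analyst neutral labels protects the comparison of scores once they exist. It does not protect the scoring. A redness grade from 0 to 3 is a judgement. Section 3.2 calls the ImageJ measurement objective, but the plan does not say that it is automated or that the operator is masked. Treating staff know the arm because one group receives IPL and the other does not, and by appointment 4 three treatments have been given. Nothing in the plan stops those staff from scoring the final images.

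This matters more because OSDI is self-reported by participants who, without a sham, can tell which treatment they received. In such a trial, outcomes that can be shielded from expectation deserve to be. Stored images are easy to shield, since they can be read away from the visit. The protocol already accepts the principle by masking the laboratories and the analyst.

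**Working it through.** **Reading the text.** Four steps lead to the gap.

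1. Who is masked (2.3): the biomarker laboratory, the microbiome laboratory and the data analyst.
2. What the analyst's masking covers (2.4): statistical analysis of collected data under two group labels. Coding or reading of images is not mentioned.
3. Who produces the redness and atrophy scores (3.2): not stated, and no masking is required.
4. Whether the arm is concealed in the clinic (6.0 and 7.0): no, because no sham is described.

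A site could therefore follow the plan exactly and still have these images scored by someone who knows the arm.

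**Which images are exposed.** Sections 2.1 and 2.2 use baseline meibography for eligibility (no more than 50% atrophy), and 2.3 randomizes only after the inclusion criteria are met. That first meibography read precedes allocation and cannot be influenced by it. The exposure is therefore mainly at appointment 4. It extends to appointment 1 if images are stored and read together later.

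**Size, as an illustration.** The plan states no figure to reproduce: section 2.5 has only a placeholder heading for the power calculation, with no alpha, test, effect size or SD. The inputs are:

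- n = 10 per arm (2.3);
- a two-sided 5% two-sample t test (assumption);
- no true effect (assumption);
- a reader shift of b SD towards IPL (assumption; the documents give no value).

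Degrees of freedom are 10 + 10 − 2 = 18, so the critical value is 2.101. The noncentrality is b × √(10/2) = 2.236 b. The rejection rate is P(T > 2.101) + P(T < −2.101), where T is noncentral t on 18 df.

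| Assumed shift b (SD) | Noncentrality | Rejection rate |
|---|---|---|
| 0 | 0 | 5.0% |
| 0.10 | 0.224 | 5.5% |
| 0.25 | 0.559 | 8.3% |
| 0.35 | 0.783 | 11.5% |
| 0.50 | 1.118 | 18.5% |

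These rates apply to each outcome separately. One value of b need not suit both: a 0 to 3 grade is probably easier to shift than a measured area percentage.

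**Reading load.** 20 patients × 2 visits = 40 patient-visits, or 40 × 2 = 80 eye-level image sets if both eyes are read (assumption).

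**The case against.** Several points on the other side have force.

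- *The masked analyst might include image readers.* The protocol uses the same verb for working on redness images. However, 2.4 describes statistical analysis by group label, which is the more natural reading. If readers are meant, a sentence should say so.
- *The plan never says that clinic staff score the images.* That is right. A reader might infer that unmasked staff will do it, and the documents do not support that. They leave the reader unspecified, so the defect is that unmasked reading is permitted.
- *Other outcomes are less exposed.* Tear osmolarity and Lipiview are numerical instrument readings, and the laboratory markers are already masked. It would be too strong to call redness and meibography the only or main outcomes that can be protected.
- *Slit-lamp images.* A reader might extend the point to all slit-lamp imaging. Apart from Keratograph redness, section 3.2 defines no score and no directional hypothesis for it, so there is nothing specified to read under mask.
- *Staining and TBUT.* One might conclude that these are graded unmasked. The examiner is not identified, and evaluation is listed before treatment at appointments 2 to 4, so a masked examiner is possible. The plan does not provide for one.
- *Masked reading may not be free.* The trainee's time and ability to grade images are not documented. Baseline meibography must be read at enrolment for eligibility, so a shuffled batch read means reading it twice. Both points stand and are reflected in the remedy.
- *The shift is assumed.* This also stands. With a small shift the effect on the error rate is negligible.

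**Conclusion.** The concern holds for two outcomes, Keratograph redness and meibographic atrophy, mainly at appointment 4. The plan masks the laboratories and the statistical analysis but not the production of these scores, in a trial without a sham and with a stated expectation in favour of MGX with IPL. That leaves a route for expectation bias, though the documents do not show that bias will occur.

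The size is conditional. If knowledge of the arm shifts readings by 0.25 to 0.5 SD, the false-positive rate per outcome is about 8% to 19% instead of 5%; at 0.1 SD it is 5.5%. These rates rest on the assumed shift, a two-sided 5% t test and 10 per arm; only the sample size comes from the plan. ImageJ measurement is likely to be less exposed than the redness grade, but that reduces the risk without supplying masking. The point is worth correcting because the correction changes no treatment, visit or sample size.

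**What to change.** Add the following to sections 2.3 and 3.2:

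1. Redness and meibography images from appointments 1 and 4 are exported under a code, with arm and visit removed, and shuffled.
2. An existing team member masked to arm reads them before group codes are linked. The blinded trainee could do this if trained in both measurements.
3. The meibography read made before randomization is used for eligibility only. The masked re-read of the baseline image enters the analysis.

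The report should state that OSDI was not masked to participants, and that staining and TBUT were not masked unless the examiner was kept unaware of the arm. Image coding does not help those measures.

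**Cost.** Coding and reading for about 40 patient-visits, which includes a second read of the 20 baseline meibography sets, and a short delay before image scores are available. Some training may be needed if the trainee is the reader. The sample size stays at 20.
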